## METHODS OVERVIEW

We will enroll patients diagnosed with COPD both in the hospital and clinic setting and follow for 30 days. Participants will complete comparative lung function measurements with both devices while in the hospital or clinic at time of enrollment and at the 30-day follow up visit. Correlation will be assessed using Spearman's correlation coefficient. A high correlation ( $> 0.8$ ) will demonstrate the usefulness of the SpiroPD device in these patients in both settings. We will use the FDA-cleared (K 103575) SpiroPD device for its intended use.

At the time of their initial study visit, study participants will be given a SpiroPD device for use at home following instruction in the hospital or clinic. Patient adherence to daily testing over one-month will be monitored using real-time capture Wi-Fi-data from the SpiroPD data portal. Participant surveys will ascertain barriers and facilitators of daily spirometry lung function testing, and subject attitudes and beliefs about the usefulness of this testing for self-management. Adherence to medication use and utilization outcomes will be measured using patient logs. Acute care utilization will be measured via tracking of ED visits, hospitalizations, and urgent care calls. Information will be collected at the 30 day (+/- 1 week) visit through in-person (preferred) or phone call visits (if do not show for in person visit).

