### Inpatient enrollment

Hospitalized patients with COPD will be screened using medical records. A member of the patients' inpatient care team (e.g., primary team, pulmonary consult service, COPD service) will be contacted for assent prior to approaching the patient. After consent, a trained research assistant will approach the patient and do the screening visit (V0) to ensure the patient has wireless internet and sufficient vision to see if they are eligible to continue with the remaining study visits. The research assistant will conduct both KoKo and SpiroPD spirometry with the participant no earlier than day 2 of the hospitalization. During this assessment, the research assistant will also provide the participant with training on use and function of the SpiroPD

device. They will return for a research visit at 30 days (+/- 1 week) if no clinic visit is scheduled during the 30 day research visit window. The patient will be offered a CTA/bus pass to return for their 30 day follow up. If the study participant is unable to attend the study visit in-person, we will arrange a phone call.

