### Survey Data Collection

Trained research staff will assess the following at the initial enrollment, post-discharge follow-up visit (for hospitalized patients), and at the 30-day follow-up:

- Demographics
- Self-reported health care utilization
- respiratory symptoms/morbidity
  - o Modified Borg Dyspnea Scale
  - o Modified Medical Research Council (MMRC) Dyspnea Scale
  - o COPD Assessment Tool
- Self-reported medication adherence
  - o MARS
- Quality of Life
  - o St. George's Respiratory Questionnaire-COPD
- Health Literacy: Ask brief health literacy screen questions for all participants
  - Brief Health Literacy Screen (BHLS) – three questions
    - o How often do you have problems learning about your medical condition because of difficulty understanding written information?
    - o How confident are you filling out medical forms by yourself?

- How often do you have someone help you read hospital material?
- SpiroPD use
  - SpiroPD Pre-Education Survey
  - SpiroPD Post-Education Survey
  - SpiroPD Follow-Up Survey
  -
- Assess vision with Snellen Chart
  - Chart should be two chart lengths away from participant
  - Ask participant to cover their right eye and use their left eye to read the smallest line they can from the chart
  - Ask participant to cover their left eye and read the smallest line they can with their right eye
  - Administrator should follow patient's reading on a copy of the chart included in forms
  - Record acuity in right and left eyes
  - If vision is not better than 20/40 in at least one eye attempt to correct vision with non-prescription glasses
    - 4 strengths of glasses: 2.00, 2.25, 2.75, and 3.25
    - Start with 2.00, and repeat the vision screen, with each eye separately
    - If visual acuity of 20/40 is reached in at least one eye, the patient is eligible to complete the STOHFLA HL evaluation using the readers
  - If vision is not corrected after trying all of the strengths of the readers, the patient is ineligible to complete the STOHFLA HL evaluation

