## **Medical Record and Administrative Data Collection**

The following data will be collected by the CRDW and merged with survey and device data:

- Admission labs (e.g., bicarbonate, hemoglobin, creatinine) (hospitalized patients)
- Admission and discharge medications, inpatient medications (hospitalized patients)
- Admission length of stay (hospitalized patients)
- Admit and discharge service (hospitalized patients)
- Procedures during hospital stay (ICD-10 coded procedure) (hospitalized patients)
- Index admission type (urgent or emergent vs elective) (hospitalized patients)
- Comorbidities, ICD-9 & ICD-10
- Number of ED visits in the 12 months prior to enrollment and during the study period
- Number of hospitalizations in the 12 months prior to enrollment and during the study period
- Number and type of outpatient visits in the 12 months prior to enrollment and during the study period

- Number of observation stays in the 12 months prior to enrollment and during the study period
- PFTs
- Prescriptions for medications
- EPIC Healthy Planet data, including follow up phone calls, medication education, etc
- Consults received
- Insurance types
- Cost accounting system data (eSimon) including expected pay, net expected pay, etc.

These data will be collected from the time of electronic medical record initiation at University of Chicago (11/1/2008) until 90 days past enrollment.

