## **DATA SAFETY MONITORING PLAN**

The PI will review monthly data reports reviewing recruitment, consent, intervention activities, adverse events, and follow-up. Although few, if any, intervention-related adverse events are anticipated in this observational study, the study population is at risk for poor outcomes, including life-threatening exacerbations and death. The PI will comply with prompt reporting of any unanticipated events to the IRB.

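### The plan never says which source defines acute care utilization; the one METHODS OVERVIEW names, patient logs, may be least complete where hypothesis (3) needs it

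*Combined protocol and SAP*

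**What the plan says.** The combined protocol and SAP describes utilization data in several places.

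- **METHODS OVERVIEW** gives logs as the measure: "Adherence to medication use and utilization outcomes will be measured using patient logs". The next sentence reads "Acute care utilization will be measured via tracking of ED visits, hospitalizations, and urgent care calls" and names no source for the tracking. The paragraph closes with the timing: "Information will be collected at the 30 day (+/- 1 week) visit through in-person (preferred) or phone call visits".
- **Inpatient enrollment** and **Outpatient enrollment** give one fallback for a missed visit: "If the study participant is unable to attend the study visit in-person, we will arrange a phone call". Nothing is said about participants who die or cannot be reached by phone.
- **Survey Data Collection** lists "Self-reported health care utilization". The Study Schema places it at baseline and at the 30-day follow-up. Neither section lists a patient log.
- **Medical Record and Administrative Data Collection** opens with "The following data will be collected by the CRDW and merged with survey and device data". Its items include "Number of hospitalizations in the 12 months prior to enrollment and during the study period", with matching items for ED visits and observation stays. The data come from the University of Chicago record and run to 90 days past enrollment.
- **PURPOSE & HYPOTHESIS**, hypothesis (3), expects acute care utilization to fall significantly in patients who adhere to home testing.
- **STATISTICAL ANALYSES**, SA2, treats acute care utilization as an estimate of efficacy, to be described statistically. It names no data source, no window and no rule for participants without day-30 information.

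**The concern.** A log or an interview yields data only if the participant keeps the log and is reached. The DATA SAFETY MONITORING PLAN recognises that "the study population is at risk for poor outcomes, including life-threatening exacerbations and death", and people with such outcomes are among those least likely to hand in a log or take a call. Keeping a log also plausibly needs the same daily engagement as home spirometry. Ascertainment of the outcome may therefore depend on adherence, which is the variable hypothesis (3) relates it to. A difference between adherent and non-adherent participants could then be created or hidden by who reports, with no true difference in utilization.

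Descriptive analysis does not remove this, because a descriptive rate is distorted in the same way. The background section says the pilot is meant to set up next-step studies and grant applications, so these estimates will be carried forward.

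**Working it through.** The documents state no event rate, log-return rate or day-30 loss, so there is no plan figure to reproduce. The check is a comparison of sections, followed by an illustration under stated assumptions.

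**Sections side by side**

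| Feature | Logs / self-report | Record extract |
|---|---|---|
| Depends on participant contact | Yes | No |
| Components named | ED visits, hospitalizations, urgent care calls (listed under tracking, source not stated) | ED visits, hospitalizations, observation stays |
| Reach | Any provider, if reported | University of Chicago only |
| Period | To the day-30 contact, which may fall on days 23 to 37 (30 ± 7) | 12 months before enrollment, then the study period; extract runs to day 90 |
| Form | Not specified | Numbers of events; dates not listed |

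The start of follow-up also varies. DURATION counts device use from discharge or from the day after the clinic visit, but counts study participation from enrollment. DATA SHARING promises a pre/post utilization summary. A log kept during the study cannot supply the pre period, whereas the record extract covers both periods by one method.

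**Illustration 1: overall under-count if day-30 reporting were the only source.** Let L be the share with no day-30 information and k their event risk relative to those seen. Both are assumptions. The share of participants with events who are missed is kL / (1 − L + kL).

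| L | k = 1 | k = 2 | k = 3 |
|---|---|---|---|
| 10% | 10% | 18% | 25% |
| 20% | 20% | 33% | 43% |
| 30% | 30% | 46% | 56% |

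Example with the planned 150 participants, an assumed 25% with an event, L = 0.20 and k = 2:

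- Expected participants with events: 150 × 0.25 = 37.5.
- Proportion among those seen: 0.25 / (0.80 + 2 × 0.20) = 0.208.
- Captured: 120 × 0.208 = 25.0.
- Missed: 12.5 / 37.5 = 33%.

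**Illustration 2: the comparison in hypothesis (3).** Assume a true event proportion of 20% in both adherence groups.

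- *(a) Return differs by adherence only, 90% against 50%; absent log scored as zero events.* Adherent 0.2 × 0.9 = 18%; non-adherent 0.2 × 0.5 = 10%; ratio 1.8, against hypothesis (3).
- *(b) Same return rates; absent log treated as missing.* Both groups show 20%; ratio 1.0.
- *(c) Adherent participants return logs at 90% without an event and 70% with one; non-adherent at 50% regardless; absent log treated as missing.* Adherent 0.2 × 0.7 / (0.2 × 0.7 + 0.8 × 0.9) = 0.14 / 0.86 = 16.3%; non-adherent 20%; ratio 16.3 / 20 = 0.81, in favour of hypothesis (3).

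The three cases show that the sign and size of the bias turn on quantities and rules the documents do not give. Case (c) also shows that treating an absent log as missing does not by itself remove the problem. A source that does not depend on the participant is needed.

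**The case against.** The strongest reply is that the plan already holds what it needs. The sentence after the one about logs deals with acute care utilization by name and says it will be tracked, and that may well mean the medical record. Record counts are planned and are to be merged with the survey and device data. The Study Schema schedules record collection at baseline, during follow-up, at 30 days and at 90 days. Contact is also not confined to one occasion: the day-30 window is two weeks wide, a phone call is allowed, staff make contact at 7 days, and Survey Data Collection mentions a post-discharge visit for hospitalized patients. This is a pilot, and SA2 is mainly descriptive.

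Most of this stands, and it rules out several stronger readings a reader might infer.

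- *That events will be lost.* The documents do not show this, because study-site events of participants who die or drop out can still enter the planned dataset.
- *That readmission removes a participant.* It does not by itself prevent contact within the window or by phone.
- *That dated records of all care exist for everyone.* The plan lists numbers of events, not dates, and the University of Chicago record only.
- *That a spurious ratio of 1.8 measures the damage.* It needs a rule scoring absent logs as zero events, which appears nowhere in the documents, and it runs against hypothesis (3).

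A record-only count also has weaknesses. It misses care at other hospitals, and urgent care calls are not among the listed record items.

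What the reply does not supply is a statement of which source defines the outcome. Having record counts in the dataset does not make them the endpoint when the only source METHODS OVERVIEW names for utilization outcomes is the log.

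**Conclusion.** The point holds as an unresolved choice of source that carries a risk of bias. Logs, self-report and institutional records are all planned. No section says which defines acute care utilization for hypothesis (3) and SA2, over which window, or how they combine. Read as METHODS OVERVIEW is worded, the outcome may be absent for participants who die, cannot be reached or disengage, and its completeness may depend on adherence.

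No size or direction can be given from the documents. The illustrative range of 10% to 56% of participants with events missed assumes that day-30 reporting is the sole source, that 10% to 30% have no day-30 information, and that their event risk is one to three times that of those seen. With the planned extract used for everyone, study-site events would not depend on contact; care elsewhere would still rest on self-report. The change should be made, because a less vulnerable source is already being collected.

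**What to change.** In METHODS OVERVIEW and in SA2 of STATISTICAL ANALYSES:

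1. Define acute care utilization, for all enrolled participants, as ED visits, hospitalizations and observation stays from the planned CRDW extract.
2. Have event dates pulled, and apply one fixed window to everyone, for example 30 days from the start of home use, whether or not a log or day-30 contact exists.
3. Use logs and self-report to add care received elsewhere and urgent care calls. Report the record-only count and the record-plus-self-report count side by side.
4. Treat an absent log as missing, not as zero events. State how deaths within the window and participants never reached are handled, and report log return and day-30 contact by adherence group.
5. Align the component lists in METHODS OVERVIEW and Medical Record and Administrative Data Collection, stating where observation stays and urgent care calls are counted.

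The cost is protocol wording and the addition of event dates to an extract that already runs to day 90. The downside is that the record-only count misses care at other hospitals, which is why both counts should be shown.

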### Inpatient enrollment

Hospitalized patients with COPD will be screened using medical records. A member of the patients' inpatient care team (e.g., primary team, pulmonary consult service, COPD service) will be contacted for assent prior to approaching the patient. After consent, a trained research assistant will approach the patient and do the screening visit (V0) to ensure the patient has wireless internet and sufficient vision to see if they are eligible to continue with the remaining study visits. The research assistant will conduct both KoKo and SpiroPD spirometry with the participant no earlier than day 2 of the hospitalization. During this assessment, the research assistant will also provide the participant with training on use and function of the SpiroPD

device. They will return for a research visit at 30 days (+/- 1 week) if no clinic visit is scheduled during the 30 day research visit window. The patient will be offered a CTA/bus pass to return for their 30 day follow up. If the study participant is unable to attend the study visit in-person, we will arrange a phone call.

### **Outpatient enrollment**

Patients being seen in the Pulmonary Clinic will be approached for participation following their clinic visit. As with the inpatient study, a trained research assistant will do a preliminary screening (wireless internet, vision) to see if the patient is eligible for the study. The research assistant will conduct obtain KoKo data from the clinical visit the patient just completed and SpiroPD spirometry with the participant. During this assessment, the research assistant will also provide the participant with training on use and function of the SpiroPD device. Outpatients will be offered a CTA/parking pass, if they decide to enroll but cannot complete the visit on the day of enrollment to return for the first visit. They will return for a research visit at 30 days (+/- 1 week) if no clinic visit is scheduled during the 30 day research visit window. The patient will be offered a CTA/bus pass to return for their 30 day follow up. If the study participant is unable to attend the study visit in-person, we will arrange a phone call.

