## **Spirometry**

Spirometry will be performed using the portable KoKo spirometer and the SpiroPD device. We have previously demonstrated that this population has poor perception of airflow obstruction and spirometry is feasible during the inpatient setting.

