## **TYPE AND NUMBER OF EXPERIMENTAL SUBJECTS**

We will enroll 150 study participants.

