### **Exclusion Criteria**

1. Currently in an intensive care unit
2. Physician declines to provide consent
3. Patient unable to provide consent (e.g., history of cognitive impairment, unable to understand English) or declines to provide consent

For our study regarding correlation of the Koko with the SpiroPD devices to measure lung function, we will have power to detect a small to moderate effect size ( $p=0.023$ ) at  $>80\%$  ( $87\%$ ) power with  $n=150$  participants at an alpha  $<0.05$ .

Statistical Test (Spearman)	Sample Size	Power	Correlation	Significance Level
Correlation	193.78	0.8	0.2	0.05
Correlation	145.92	0.8	0.23	0.05
Correlation	123.13	0.8	0.25	0.05
Correlation	84.75	0.8	0.3	0.05

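### Clinic recruits' KoKo value is only retrieved from the clinic visit, so some baseline device pairs may be missing or split across days; the cost falls mainly on the clinic-setting comparison

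*Combined protocol and SAP*

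**What the plan says.** - Methods Overview applies to everyone: "Participants will complete comparative lung function measurements with both devices while in the hospital or clinic at time of enrollment", and again at the 30-day visit. The Study Schema marks spirometry at both times.
- Spirometry: "Spirometry will be performed using the portable KoKo spirometer and the SpiroPD device".
- Inpatient enrollment puts this into practice: "The research assistant will conduct both KoKo and SpiroPD spirometry with the participant".
- Outpatient enrollment does not. There the assistant is to "obtain KoKo data from the clinical visit the patient just completed and SpiroPD spirometry with the participant". The same section offers travel support to patients "if they decide to enroll but cannot complete the visit on the day of enrollment to return for the first visit".
- Inclusion Criteria ask that the patient can perform spirometry. They do not ask that a KoKo test was done at the clinic visit.
- The 30-day visit may be replaced by a phone call.
- Type and Number of Experimental Subjects: "We will enroll 150 study participants". The power statement after Exclusion Criteria uses the same 150, with no allowance for missing pairs.
- Statistical Analyses (SA1) names Spearman's coefficient and the threshold of 0.8. It does not say which visit's pairs are analysed or whether the two tests must come from one session.

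**The concern.** Staff recruiting in clinic will work from the Outpatient enrollment section, and it leaves two gaps.

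1. If the clinic visit included no KoKo test, no comparator exists at baseline, and no fallback is written.
2. If the first study visit is deferred, the only KoKo value the section names is the one from the earlier clinic visit. The two devices are then read on different days, and real change in lung function between the days is mixed with disagreement between the devices.

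Neither can be repaired at analysis. The loss is also unlikely to be random. Clinic patients who keep a baseline pair are those whose visit happened to include spirometry. The documents do not allow the direction or size of that selection to be judged. It matters because the Aim 1 hypothesis names ambulatory as well as hospitalized patients, and Methods Overview claims usefulness in both settings.

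**Working it through.** **1. The plan's own sample-size figure.** For one correlation tested against zero, two-sided alpha 0.05 and 80% power, Fisher's z gives n = ((1.960 + 0.842) / atanh(ρ))² + 3.
- ρ = 0.23: atanh = 0.2342, so n = 146.1. The plan's row (n, power, correlation, alpha) is "145.92 0.8 0.23 0.05".
- ρ = 0.25: atanh = 0.2554, so n = 123.3. The plan's row is "123.13 0.8 0.25 0.05".

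The table reproduces to within 0.2.

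**2. Which row the power statement uses.** The text prints an effect size of 0.023 and power of 87% at n = 150. By Fisher's z, two-sided, power at n = 150 is about 6% for 0.023, 81% for 0.23 and 87% for 0.25. So 87% fits 0.25, while the printed effect size looks like a misprint of 0.23. Losses that still leave 80% power:
- at 0.23: 150 − 145.92 = 4.08, so 4 pairs
- at 0.25: 150 − 123.13 = 26.87, so 26 pairs

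**3. Scenarios.** The documents give neither the clinic share nor the share of clinic visits without a KoKo. Assume a clinic share of one half (75 of 150) and 10%, 25% or 50% of those unpaired. Pairs left: 150 − 7.5, 150 − 18.75 and 150 − 37.5, rounded down to 142, 131 and 112.

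| Pairs | Power at 0.23 | Power at 0.25 |
|---|---|---|
| 150 | 81% | 87% |
| 142 | 79% | 85% |
| 131 | 75–76% | 82% |
| 112 | 69% | 76% |

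The small ranges come from two versions of the approximation.

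**4. The criterion that decides Aim 1.** The table concerns a test against zero, whereas Aim 1 is judged on a coefficient above 0.8. At a true correlation of 0.8, power against zero is essentially 100% at n = 150. Precision is the relevant quantity. The Bonett–Wright 95% interval for Spearman's coefficient is tanh(atanh(r) ± 1.96 × √((1 + r²/2)/(n − 3))). With r = 0.85 (illustrative), atanh(r) = 1.2562 and 1 + r²/2 = 1.36125.

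| Pairs | 1.96 × SE | 95% interval |
|---|---|---|
| 150, whole sample | 0.189 | 0.789 to 0.895 |
| 112, whole sample | 0.219 | 0.777 to 0.901 |
| 75, clinic only | 0.270 | 0.756 to 0.910 |
| 56, clinic only (25% unpaired) | 0.314 | 0.736 to 0.917 |
| 37, clinic only (50% unpaired) | 0.392 | 0.698 to 0.929 |

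The whole-sample interval grows from 0.106 to 0.124 wide. The clinic interval grows from 0.154 to 0.231 wide, about half as wide again.

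**5. Chance of meeting the criterion.** On the same approximation, if the true value is 0.85, the observed whole-sample coefficient exceeds 0.8 with probability about 95% at 150 pairs and 93% at 120.

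**The case against.** The best reply is that Methods Overview and Spirometry already require both devices. On that view the Outpatient enrollment sentence, which is garbled as printed, takes for granted that a KoKo result exists from the visit just completed. Nothing in the documents shows that clinic visits without a KoKo are common, and this is a single-center pilot. That much stands: the gap is inferred from silence, and every loss rate above is an assumption. The reply does not remove the conflict between the general sections and the operating instruction for clinic, nor does it deal with the deferred visit.

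A reader might also infer more than the documents support:
- *That a clinic recruit without a baseline KoKo cannot contribute to Aim 1.* Two-device spirometry is planned again at 30 days, and SA1 is not limited to baseline. An in-person 30-day visit could supply a pair; a phone call could not.
- *That the power claim survives only about 4 losses.* That holds for the 0.23 row alone. The stated 87% fits 0.25, where about 26 losses keep 80%.
- *That enrolled patients who never received a device would be scored as non-adherent.* SA2 sets no denominator, so this cannot be read from the plan.
- *That all avoidable loss lies in clinic.* Inpatient testing waits until at least day 2 of the stay, so inpatients could be missed too.

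**Conclusion.** The concern holds as a conflict between sections that puts clinic baseline pairs at risk of being missing or split across days. It is not a threat to the overall Aim 1 result: even with 112 pairs the whole-sample interval is close to that with 150, and the stated power is for a test that does not decide Aim 1. The cost falls on the clinic-setting comparison, through selection of unknown direction and lower precision. With half the sample from clinic and half of those lacking a KoKo, both assumed, about 37 of 75 clinic pairs remain and the interval for an observed 0.85 is 0.698–0.929 instead of 0.756–0.910. With a quarter lacking a KoKo it is 0.736–0.917. The change is worth making before recruitment because it is cheap and a missed baseline pair cannot be recovered.

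**What to change.** 1. Amend Outpatient enrollment: when there is no same-session KoKo result, because none was done at the clinic visit or because the first study visit is deferred, the research assistant runs the portable KoKo together with SpiroPD at the first study visit.
2. State in Statistical Analyses (SA1) that the correlation uses same-session pairs, and from which visit.
3. In the power statement, describe n as completed pairs rather than enrolled participants. While editing it, reconcile the printed 0.023, the 0.23 row and the 87%.

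The cost is protocol wording and a few minutes of assistant time per affected patient, on equipment the study already uses for inpatients. Stated power may fall slightly once n counts pairs.
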